#### Other Effective Methods

9. Progestogen-only oral hormonal contraception where inhibition of ovulation is not the primary mode of action.
10. Male or female condom, with or without spermicide.
11. Cervical cap, diaphragm, or sponge with spermicide.
12. A combination of male condom with either cervical cap, diaphragm, or sponge with spermicide (double-barrier methods).

BYOD	Bring Your Own Device
CGI-c	Clinical Global Impression-change
CI	Confidence Interval
CPK	Creatine Phospho Kinase
CRF	Case Report Form
CTCAE	Common Terminology Criteria for Adverse Events
DILI	Drug-Induced Liver Injury
EAS	Efficacy Analysis Set
ECG	Electrocardiogram
eDiary	Electronic Diary
eDISH	Drug-Induced Serious Hepatotoxicity
eGFR	Estimated Glomerular Filtration Rate
FAS	Full Analysis Set
FSH	Follicle Stimulating Hormone
FUSS	Follow-up Safety Analysis Set
HbA1c	Hemoglobin A1c
LDH	Lactate Dehydrogenase
LT	Long-Term Treatment
MDRD	Modification of Diet in Renal Disease
MedDRA	Medical Dictionary for Regulatory Activities
MIDAS	Migraine Disability Assessment
MSQoLQ	Migraine-Specific Quality of Life Questionnaire
N	Number
NCI	National Cancer Institute
ODT	Orally Disintegrating Tablet
OP	Observation Period
PoM	Preference of Medication
PRN	Pro re nata
PT	Preferred Term
SAE	Serious Adverse Event
SAP	Statistical Analysis Plan
SS	Safety Analysis Set

SBP	Systolic Blood Pressure
SD	Standard Deviation
SM	Satisfaction with Medication
SOC	System Organ Class
TBL	Total Bilirubin
TEAE	Treatment Emergent Adverse Event
ULN	Upper Limit of Normal
WOCBP	Women of Childbearing Potential
WHO-DD	World Health Organization Drug Dictionary

1 Introduction

This Statistical Analysis Plan is based on the final study protocol BHV3000-318 (Protocol Version 5.0, dated 18Aug2023) and final case report form (CRF, Version 3.0, dated 21Mar2023). For the details for interim analysis, refer to Interim Analysis Plan (Version 1.0, dated 11Apr 2023).

2 STUDY OBJECTIVES

2.1 Primary Objective

To evaluate the long-term safety and tolerability of 75 mg Rimegepant ODT [dosed as needed (PRN)].

2.2 Secondary Objective

To evaluate the number of migraine days and severity of migraine attacks during long-term treatment (LT) with 75 mg Rimegepant ODT (PRN) in participants compared to the observation period (OP).

2.3 Exploratory Objectives

- To evaluate the effect of 75 mg Rimegepant ODT treatment compared to baseline on the 14-Item Migraine-Specific Quality of Life Questionnaire v 2.1 (MSQoLQ).
- To evaluate the effect of 75 mg Rimegepant ODT treatment on the Migraine Preference of Medication (PoM).
- To evaluate the effect of 75 mg Rimegepant ODT treatment on the Satisfaction with Medication (SM) survey.
- To evaluate the effect of 75 mg Rimegepant ODT treatment compared to baseline on the Migraine Disability Assessment (MIDAS).
- To evaluate the effect of 75 mg Rimegepant ODT treatment on the Clinical Global Impression-change (CGI-c) scale.

3 Study Design

3.1 Overall Design

This will be a multi-center, open-label, long-term safety study of BHV3000 for the treatment of acute migraine in Chinese participants to provide the long-term safety data in Chinese participants to bridge the existing comprehensive clinical trial data of 75 mg Rimegepant in migraine. Approximately 240 adult participants with migraine were planned to be enrolled to receive 75 mg of Rimegepant ODT (PRN use, up to 1 tablet per day).

The screening period will be consisted of a screening visit and a 30-day OP. Participants must have a history of 6 to 18 moderate to severe migraine attacks per month within 3 months prior to the Screening Visit in order to meet the entering criteria of this study.

Upon the completion of the screening visit, participants will be provided an electronic diary (eDiary) to document each day if a migraine occurs, the intensity of each migraine attack and

if the migraine is treated for the 30-day OP. Participants will record the standard of care migraine treatment received via bring your own device (BYOD). After completing the 30-day OP, the participant will return to the clinic with both records for the Baseline Visit. At the Baseline Visit, eligibility for continued participation in the study will be assessed, and eligibility will be determined as much as possible prior to dispensing study drug, participant need have least 6 migraine days during the 30-day OP to be eligible and women of childbearing potential (WOCBP) must have a negative pregnancy test result prior to dispensing study drug. After the investigator reviews the results of the baseline laboratory assessments and determines the participant's continued eligibility, the site staff will inform the participant whether or not he/she is eligible to start dosing in the LTT Phase. If eligible for the LTT, participants will be instructed that they can take study medication at the onset of a migraine (of mild to severe intensity). Participants will be instructed that they can take a maximum of one tablet of Rimegepant per calendar day during the 52-week LTT Phase at the onset of a migraine (of mild to severe intensity).

Participants are required to record their migraine occurrence and severity in the eDiary, to record all study medication doses via BYOD. Participants are also required to continue to record the standard of care migraine treatment taken via BYOD. Participants will also use BYOD to complete the PoM questionnaire and the SM questionnaire at specified study timepoints.

[figure not shown]
At selected study visits, participants will complete or will be administered the MSQoLQ v 2.1, the MIDAS, and CGI-c scale.

Procedures include study personnel review of the eDiary and BYOD with the participant, assessment of study medication compliance, monitoring of tolerability and safety (including vital signs, laboratory tests, and electrocardiography). Study visits will be approximately every 4 weeks until Week 16 and then every 12 weeks for on-site visits + every 4 weeks phone calls in between every two on site visits until Week 52.

Participants will return to the study site at the end of Week 52 (\pm 7 days) for the End of Treatment Visit. There is a Follow-up Visit 14 days (\pm 2 days) after the Week 52/Early Termination Visit.

The overall study design schematic is shown in Figure 1.

Figure 1 Study Design

3.2 Randomization

Not applicable.

3.3 Blinding

This study is a single-arm trial. Blinding and unblinding methods are not applicable.

3.4 Sample Size Calculation

The sample size for this study is primarily based on historical data, considering the safety evaluation and estimation precision for the secondary endpoint. For the secondary endpoint of change from observation period in the number of migraine days per month from Week 9-12 in participants treated with rimegepant, data from previous long-term migraine study BHV3000-201 showed:

- 848 participants with a history of 6-18 days of migraine within 3 months prior to baseline.
- Mean (standard deviation, SD) baseline migraine days: 9.92 (3.09).
- Migraine days mean (SD) Weeks 9-12: 8.84 (4.97).
- Change from baseline in mean (SD) number of migraine days at weeks 9-12: -1.08 (4.74).

Based on the above historical trial data results and a t distribution assumption, in this single-arm study, 205 evaluable participants will provide a 90% power to observe a negative change from baseline in migraine days at Weeks 9-12 for a 1-sided 2.5% significance level, and finally 233 participants are required to be included considering 12% dropout rate based on BHV3000-201 trial. Considering other possible data loss, approximately 240 participants will be finally

enrolled.

In the case of 240 participants, if the adverse event rate is 5% and 1%, then the probability of observing at least one adverse event is >99.9% and 91.0%, respectively, thus providing sufficient information for safety and tolerability assessment after LTT with 75 mg rimegepant ODT in Chinese participants to bridge the available comprehensive clinical trial data of rimegepant 75 mg in the treatment of migraine.

4 Study Endpoints

4.1 Primary Endpoints

- Adverse events, common AEs (incidence $\geq 5\%$), serious adverse events (SAE), adverse events leading to study drug discontinuation, etc.; ECG, vital signs/physical measurements and clinical laboratory test abnormalities.

4.2 Secondary Endpoint

- Change from Observation Period in the number of migraine days by total and moderate or severe pain intensity for every 4-week interval and overall period during long-term treatment with 75 mg rimegepant ODT.

4.3 Exploratory Endpoints

- Change from baseline in results assessed with the 14-item MSQoLQ version 2.1 following treatment with 75 mg rimegepant ODT.
- Percentage of participants in each of 3 preference categories of the assessment with Migraine PoM for migraine following treatment with 75 mg rimegepant ODT.
- Percentage of participants in each of 7 satisfaction categories of the SM survey following treatment with 75 mg rimegepant ODT.
- Change from baseline in total score of the MIDAS following treatment with 75 mg rimegepant ODT.
- Percentage of participants in each of 7 categories of the CGI-c scale after treatment with 75 mg rimegepant ODT.

5 STUDY HYPOTHESIS

The statistical analysis is mainly descriptive, and no formal hypothesis testing will be performed.

6 ANALYSIS SETS

The following analysis sets will be determined:-

- Screened participants set: All participants who sign the informed consent. It will be used for the analysis of participant disposition.
- Enrolled participants set: Participants with an available date collected in the CRF on

which the investigator judges that they can be enrolled and notifies of their eligibility to start taking the investigational product by phone. It will be used for the analysis of participant disposition and drug accountability.

- Full analysis set (FAS): All participants who are enrolled and received at least one dose of the investigational product. It will be used for the analysis of baseline characteristics, as well as the analyses of exploratory endpoint measures.
- Efficacy analysis set (EAS): All participants in the FAS with ≥ 14 eDiary days (not necessarily consecutive) in both the OP analysis period and ≥ 1 month (4-week interval) of the LTT analysis period. The EAS will be used to assess the secondary endpoint.
- Safety analysis set (SS): All participants who received at least one dose of investigational product. The SS will be used for safety analyses during treatment safety period.
- Follow-up safety analysis set (FUSS): All participants in the SS with last contact date (see [Section 7.2.3](#)) in the follow-up safety analysis period. The FUSS will be used for follow-up safety analyses.

7 STATISTICAL METHODOLOGY AND CONVENTIONS

7.1 General Methods

All relevant data of all participants entered into the database will be included in the participant data listings. Unless otherwise specified, participant listings will be ordered by site, participant ID, and other variables (e.g., time point). The listings will indicate the site-participant ID.

For categorical variables, a summary table of the number and percentage of participants in each category will be presented, and the category of missing data will be provided. For continuous variables, the descriptive statistics of n (e.g., number of participants), mean, median, SD, minimum, and maximum, etc. will be presented. The minimum and maximum values will be expressed with the same precision as the data. The mean and median values will be expressed with the data precision plus one decimal place. SD will be expressed with the data precision plus two decimal places. In general, all summary statistics will be reported with a maximum of four decimal places.

The 95% confidence interval (CIs) will be calculated for these endpoints: 1) Two-sided 95% CIs based on normal distribution will be calculated for continuous endpoints, including migraine days, MSQoLQ, and MIDAS. 2) Two-sided exact Clopper-Pearson CIs will be calculated for PoM, SM, and CGI-c.

For the safety data and the efficacy data collected in the CRF, unless otherwise specified, baseline will be the last non-missing assessment data prior to or on the day of first dose. For the efficacy data collected in the eDiary, baseline will be calculated based on the data from the observation analysis period.

SAS® (Version 9.4) will be used to perform all statistical calculations and generate tables, listings, and figures.

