#### **4.3.5. Unplanned Visit**

In consideration of the safety of the participants, the investigator may require the participants to conduct additional visits or examinations. Results of unscheduled visits or examinations will be recorded on the eCRF.

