7.2.2 Other Data Processing Rules

In the descriptive summaries of safety endpoints (e.g., absolute value and change from baseline in laboratory tests, vital signs, ECG), if an assessment is measured two or more times at a visit, then the last data of the visit will be used for analysis. The assessment results of all unscheduled and scheduled visits will be presented in the listings.

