7.2.4 Analysis Periods

To facilitate the analyses based on eDiary data (including eDiary compliance and migraine days), the analyses for safety endpoints, the following analysis periods will be defined.

Table 1. Analysis Periods

Analysis periods	Start date/time	End date/time	Usage
OP	Screening Visit date	LT _T start date – 1 day	To be used to calculate the eDiary compliance, number of migraine days per 4 weeks in this period.
LT _T	Earlier of (1) Baseline Visit date, and (2) study drug start date	Later of (1) Week 52/EOT date, and (2) study drug last dose date	To be used to calculate the eDiary compliance and number of migraine days per 4 weeks or the overall period in the long-term treatment.
Pre-treatment safety		Study drug start date – 1 day for AEs; study drug start date/time otherwise	To be used to assess the safety endpoints prior to study drug treatment.
Treatment safety	Study drug start date for AEs; after study drug start date/time otherwise	[Later of (1) Week 52/EOT date, and (2) study drug last dose date] + 7 days	To be used to assess the safety endpoints of the treatment period.
Follow-up safety	[Later of (1) Week 52/EOT date, and (2) study drug last dose date] + 8 days		To be used to assess the safety endpoints of the follow-up period.

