The number and percentage of participants with laboratory test abnormalities according to CTCAE grade (Grade 0; Grade 1-2; Grade 3-4) will be presented during the treatment (using SS) and follow-up (using FUSS) safety analysis periods, respectively. The highest CTCAE grade during the analysis period will be used. Additionally, the abnormal laboratory tests in at least 5% of overall participants or CTCAE Grade 3-4 will be summarized by average rimegepant exposure (< 2, \geq 2 to < 8, \geq 8 < 14, < 14, \geq 14 tablets per month, and overall).

The number and percentage of participants with shifts from baselines in CTCAE grades (Grade 0, 1, 2, 3, 4, 1-4) to the treatment safety period based on SS (refer to Section 7.2.4) will also be presented, using the highest CTCAE grade.

The number and percentage of participants with LFT elevations in the following categories will be presented during the treatment based on SS safety analysis period, for participants in different categories of average rimegepant exposure (< 2, \geq 2 to < 8, \geq 8 < 14, < 14 and \geq 14 tablets per month) and overall participants:

- Cumulative elevations

ALT > 1x, \geq 3x, \geq 5x, \geq 10x, and \geq 20x ULN

AST > 1x, \geq 3x, \geq 5x, \geq 10x, and \geq 20x ULN

ALT or AST > 1x, \geq 3x, \geq 5x, \geq 10x, and \geq 20x ULN

TBL > 1x and \geq 2x ULN

ALP > 1.5x ULN

These are based on the highest ratio of value to ULN for each laboratory test. Note that participants may be in > 1 category for each laboratory test.

- Mutually exclusive elevations

ALT > ULN to \leq 3x ULN, \geq 3x ULN to \leq 5x ULN, \geq 5x ULN to \leq 10x ULN, \geq 10x ULN to \leq 20x ULN, and \geq 20x ULN

AST > ULN to \leq 3x ULN, \geq 3x ULN to \leq 5x ULN, \geq 5x ULN to \leq 10x ULN, \geq 10x ULN to \leq 20x ULN, and \geq 20x ULN

These are based on the highest ratio of value to ULN for each laboratory test. Note that participants may be in only 1 category for each laboratory test.

- Composite elevations

ALT or AST > 3x ULN and TBL > 1.5x ULN. This is based on the highest ratio of value to ULN for each laboratory test.

ALT or AST > 3x ULN and TBL > 2x ULN. This is based on the highest ratio of value to

ULN for each laboratory test.

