7.5.4 Vital Signs and Physical Measurements

For each vital sign parameter (systolic blood pressure, diastolic blood pressure, pulse rate, respiratory rate, temperature) and physical measurement parameter (weight, BMI), observed values and changes from baseline will be summarized at the following timepoints: baseline, each scheduled visit, early termination, and Follow-up visit using SS. See Section 7.2.2 for handing multiple values in an analysis window.

The number and percentage of participants with vital sign abnormalities in the following categories will be presented during the treatment (using SS) and follow-up (using FUSS) safety analysis periods, respectively, for participants in different categories of average rimegepant exposure (< 2 , ≥ 2 to < 8 , ≥ 8 to < 14 , < 14 and ≥ 14 tablets per month) and overall participants:

Individual listing will be provided using SS.

Systolic BP (mm Hg)	min. < 90	
Systolic BP (mm Hg)	max. > 140	
Systolic BP (mm Hg) change from baseline	max. decrease ≥ 30	max. increase ≥ 30
Diastolic BP (mm Hg)	min. < 50	
Diastolic BP (mm Hg)	max. > 90	
Diastolic BP (mm Hg) change from baseline	max. decrease ≥ 20	max. increase ≥ 20
Pulse rate (beats/min)	min. < 40	max. > 120

7.5.5 12-lead ECG

For each 12-lead ECG parameter (heart rate, PR interval, QRS duration, QT interval, and QTcF), the observed values and changes from baseline will be summarized at the following timepoints: baseline, each scheduled visit, early termination, and Follow-up visit using SS. See Section 7.2.2 for handing multiple values in an analysis window.

The number and percentage of participants with ECG abnormalities in the following categories will be presented during the treatment safety (using SS) and follow-up (using FUSS) safety analysis periods, respectively, for participants in different categories of average rimegepant exposure (< 2, \geq 2 to < 8, \geq 8 < 14, \geq 14 and \geq 14 tablets per month) and overall participants:

- QTcF (msec): \leq 450, 450 - \leq 480, 480 - \leq 500, $>$ 500
- QTcF increase from baseline (msec): \leq 30, 30 - \leq 60, $>$ 60.

Individual listing will be provided using SS.

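### The SAP sets the safety baseline by calendar day but the treatment period by clock time, so a post-dose reading on the first-dose day can serve as baseline (minor; rare case)

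*SAP*

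**What the plan says.** Two SAP rules govern a reading taken on the day of the first dose.

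- **Baseline (SAP 7.1).** For safety data, unless otherwise specified, "baseline will be the last non-missing assessment data prior to or on the day of first dose". The unit is the calendar day.
- **Analysis periods (SAP 7.2.4, Table 1).** For data other than adverse events, the pre-treatment safety period ends at the "study drug start date/time otherwise". The treatment safety period begins as follows: "Study drug start date for AEs; after study drug start date/time otherwise". The unit is date and time.

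SAP 7.5.3 to 7.5.5 give no other baseline definition for laboratory tests, vital signs or ECG. SAP 7.2.2 adds that "if an assessment is measured two or more times at a visit, then the last data of the visit will be used for analysis", which chooses among repeats within one visit and does not require a pre-dose value.

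Baseline feeds several outputs tied to the primary safety endpoint:

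- blood pressure, for example "Systolic BP (mm Hg) change from baseline", with classes at 30 mm Hg systolic and 20 mm Hg diastolic (SAP 7.5.4);
- QTcF increase, with cut-points at 30 and 60 msec (SAP 7.5.5);
- "The number and percentage of participants with shifts from baselines in CTCAE grades", and the corresponding liver-test shifts (SAP 7.5.3);
- changes from baseline at each scheduled visit.

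**The concern.** Table 1 separates pre-dose from post-dose readings within the first-dose day. The baseline rule in SAP 7.1 does not. A post-dose reading that is the last of that day belongs to the treatment period and also becomes the value against which treatment-period readings are judged. Its own change is then zero by construction, and the pre-dose value drops out of every comparison for that participant.

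Abnormalities in ECG, vital signs and laboratory tests are part of the primary endpoint. The tables that express them relative to baseline would be wrong for such a participant, and nothing in the tables would show it.

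**Working it through.** The plan states no figure for this point, so there is none to reproduce. The check has two parts.

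**1. Can the case arise?** The protocol (Table 1 footnote 1; 4.3.2; 7.2.2) sets this order: Baseline Visit assessments, confirmation of eligibility by telephone, then a first dose at a migraine attack. The schedule has no assessment tied to the first dose. A post-dose reading on that day therefore needs one of three routes:

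- an unscheduled examination, since under Protocol 4.3.5 "the investigator may require the participants to conduct additional visits or examinations" for safety reasons;
- a later site visit that falls on a delayed first-dose day;
- dosing out of sequence, before the Baseline Visit assessments. The SAP allows for this: Table 1 starts the long-term treatment period at the earlier of the Baseline Visit and the first dose, and the disposition table (7.3.1) has a row for participants treated without being enrolled.

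All three are possible, and none is expected often.

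**2. What do the rules give when it does?** Take one constructed participant. All values are assumed and serve only to show the mechanism.

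| Reading | SBP (mm Hg) | QTcF (msec) |
|---|---|---|
| Baseline Visit, a week before the first dose | 120 | 420 |
| Unscheduled, 2 hours after the first dose, same day | 155 | 485 |
| Week 4 visit | 122 | 422 |

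Change = treatment-period reading − baseline. Under Table 1, the second and third readings are treatment-period data whichever baseline is used. It is assumed that the class tables use all readings in the period; SAP 7.5.4 and 7.5.5 do not restrict them to scheduled visits.

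*Calendar-day baseline (SAP 7.1 as written):* baseline is 155 / 485.

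- SBP changes: 155 − 155 = 0; 122 − 155 = −33. The maximum increase is 0, and the maximum decrease is 33, which meets the class of 30 or more.
- QTcF changes: 485 − 485 = 0; 422 − 485 = −63. The maximum increase is 0.

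*Date-and-time baseline (consistent with Table 1):* baseline is 120 / 420.

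- SBP changes: 155 − 120 = +35; 122 − 120 = +2. The maximum increase is 35, which meets the class of 30 or more. There is no decrease.
- QTcF changes: 485 − 420 = +65; 422 − 420 = +2. The maximum increase is 65, in the class above 60.

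| Output | SAP 7.1 rule | Date-and-time rule |
|---|---|---|
| SBP increase ≥ 30 | not counted | counted |
| SBP decrease ≥ 30 | counted | not counted |
| QTcF increase class | ≤ 30 | > 60 |
| Week 4 SBP change | −33 | +2 |
| SBP > 140 at any time | counted (155) | counted (155) |
| QTcF absolute class | 480 to 500 (485) | 480 to 500 (485) |

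The last two rows are identical because they do not use baseline. The CTCAE and liver-test shift tables behave like the first rows: if the post-dose value sets the baseline category, its own rise shows no shift.

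**The case against.** Four objections carry weight.

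**The case is rare.** Baseline tests come first, dosing follows a telephone call, and nothing is scheduled after the first dose. Entry requires at least 6 migraine days in the 30-day Observation Period, so a first dose delayed until the Week 4 visit should also be unusual. This stands. No frequency can be derived from the documents.

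**The reading is not lost.** It stays in the treatment safety period, so it counts towards the absolute blood-pressure and QTcF limits, the highest CTCAE grade and the multiples of the upper limit of normal. SAP 7.2.2 lists all scheduled and unscheduled results. Clinically significant abnormalities are adverse events under Protocol 8.1, and adverse events are assigned to periods by onset date. This stands too. A reader might infer that the SAP hides acute reactions; the documents do not support that.

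**The rules can coexist in code.** A reader might infer that the two rules cannot both be programmed. They can: one record can carry a baseline flag and a treatment-period flag, as the worked example does. The fault is that the two roles conflict in meaning.

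**Questionnaires are already protected.** The baseline row of SAP Table 3 is also worded by day, so a reader might extend the point to MSQoLQ and MIDAS. But the Table 3 algorithm takes the value closest to the target day (Day 1), then the one with the correct visit label. In the normal sequence Day 1 is the Baseline Visit date, so the Baseline Visit questionnaire is selected.

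Nor do the documents show that such readings come mainly from participants who reacted to the dose. That is plausible for unscheduled examinations, but a same-day reading may equally be normal.

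**Conclusion.** The point holds in a limited form. SAP 7.1 permits a post-dose, on-treatment reading to serve as the safety baseline, and no other section overrides it. It requires a post-dose reading on the first-dose day that is the last non-missing value of that day.

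For an affected participant the distortion of baseline-relative outputs can be complete: in the example, +35 mm Hg becomes 0, +65 msec becomes 0, and a fall of 33 mm Hg is counted. The direction depends on the reading. A high value lowers later changes, a low value raises them, and a normal value does little. Across the trial the effect is probably small, but the number of participants is unknown. The 120/155/122 and 420/485/422 values are assumptions, not trial data.

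The severity is minor. It merits correction because it touches tables for the primary endpoint and is better settled before programming than after results are seen.

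**What to change.** In SAP 7.1, define baseline for safety data other than adverse events as the last non-missing value at or before the study drug start date and time. This matches Table 1.

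Add a rule for first-dose-day values with no recorded time: treat scheduled Baseline Visit values as pre-dose, and unscheduled or later-visit values as post-dose. Falling back to an earlier day whenever the time is missing would be worse. It could discard a valid Baseline Visit value for a Screening value about 30 days older, and for the lipid panel, which is not collected at Screening, it would leave no baseline. Extended to MSQoLQ and MIDAS, which also have no Screening value, it would do the same.

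The Table 3 selection rule needs no change; aligning the wording of its baseline row is optional.

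The cost is a sentence or two in the SAP and a small programming change. Assessment times may not be recorded for every measurement, and the supplied documents do not show which are, so the untimed-value rule will sometimes decide. It would misclassify an untimed Baseline Visit value if the participant had dosed earlier that day, so any such participants should be identified at the data review meeting before database lock.
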